## 8.0 Statistical Plan

Descriptive statistics will be generated to describe the characteristics of different cohorts of interest. The diabetes related outcomes will be summarized at the individual level on a yearly basis. There will be binary outcomes (Yes/No) such as controlled diabetes, controlled blood pressures, receiving annual eye exam, receiving obesity and/or nutritional counseling, and count outcomes such as numbers of clinic visits, emergency department visits and hospitalization, and continuous outcomes such as cost of healthcare utilizations. The distributions of outcome measures will be examined by using minima, maxima, ranges, medians, quartiles, means, and standard deviations for continuous variables, and frequency and contingency tables for categorical variables.

To evaluate the impact of policy changes on these outcomes, we will examine how these outcomes change over time, in response to the policy changes. As descriptive analyses, we will plot the mean trajectory of each yearly outcome at clinic level, health system level and state level. The statistical modeling of patterns of changes in individual level outcomes will be carried out through multi-level mixed-effects models. The mixed-effects model is a common and popular modeling technique for longitudinal data. A mixed-effects model can accommodate within- and between-subjects variability, as well as serial correlations. In addition, it has the flexibility to incorporate time-dependent covariates, incomplete data, and heteroscedasticity of the variances and correlations. The mixed-effects model will be specified in a multi-level fashion so that different levels of variability (e.g., individual characteristics, social environment, built environment) can be taken into account. The pattern of changes in the outcome will be assessed for pre- and post-periods, respectively, based on the piecewise/segmented regression models. The slope of each segment indicates the trend of change in diabetes outcome in that period. Therefore, the change in the trend/slope post-policy implementation may reveal the actual impact of the new policy controlling for baseline level and trend. Such modeling strategies share the same spirit of interrupted time series analysis. While the classical interrupted time series design often generates a single long series of data, we have a large number of short series from each individual subject, namely, longitudinal data. Depending on the types of the outcomes, we will specify mixed-effects models based on logistic

regression for a binary outcome, Poisson regression for a count outcome and linear regression for a continuous outcome as detailed below.

In the multi-level modeling, the first-level unit is the yearly measurement for the individual subject (pre- and post-policy), the second-level unit is the individual subject, the third-level unit is the health system or clinic within the health system (cluster), and the fourth-level unit is the state. We set year 2014 as time origin for Utah when considering the policy impact of the ACA. Let  $Y_{ijkt}$  denote the binary response of having controlled diabetes at year  $t$  since policy changes for the  $k^{\text{th}}$  subject within the  $j^{\text{th}}$  cluster of the  $i^{\text{th}}$  state,  $t = -5, -4, \dots, 0, 1, \dots, 5$ ,  $i = 1, 2, 3$ ;  $j = 1, 2, \dots, c_i$ , and  $k = 1, 2, \dots, n_{ij}$ , where  $c_i$  is the number of clusters within the  $i^{\text{th}}$  state and  $n_{ij}$  is the sample size within the  $j^{\text{th}}$  cluster of the  $i^{\text{th}}$  state. An individual subject may not be in the system for all 11 timepoints of measurement, so  $t$  will have a smaller range of values for that individual subject. Also due to the different timeline of policy changes, the number of years before and after policy changes may vary. The probability of having controlled diabetes,  $\mu_{ijkt} = E(Y_{ijkt}) = \Pr[Y_{ijkt} = 1]$ , can be described by the following segmented logistic regression model

$$\begin{aligned} \text{logit } \mu_{ijkt} &= \log \{\Pr[Y_{ijkt} = 1] / \Pr[Y_{ijkt} = 0]\} \\ &= \beta_{0ijk} + (t + 5) \beta_{1ijk} && \text{if } -5 \leq t \leq 0, \text{ pre-period before policy changes} \\ &= \beta_{0ijk} + 5 \beta_{1ijk} + t \beta_{2ijk} && \text{if } 0 \leq t \leq 5, \text{ post-period after policy changes} \end{aligned}$$

where  $\beta_{mijk}$  ( $m = 0, 1, 2$ ) are subject-specific regression parameters, with  $\beta_{0ijk}$  being the log odds of having controlled diabetes at  $t = -5$ , and  $\beta_{1ijk}$  and  $\beta_{2ijk}$  being the slopes (annual change in log odds) for the pre- and post-periods, respectively. In the framework of a mixed-effects model, each  $\beta_{mijk}$  is modeled by

$$\beta_{mijk} = \mathbf{x}_{mijk}^T \boldsymbol{\beta}_m + \mathbf{z}_{ij}^T \boldsymbol{\gamma}_{1ij} + \boldsymbol{\gamma}_{2mijk}$$

where  $\mathbf{x}_{mijk}$  is the vector of regressors for the fixed effects,  $\boldsymbol{\beta}_m$  is the corresponding vector of fixed-effects parameter coefficients,  $\mathbf{z}_{ij}$  is a vector of cluster-level regressors for the random effects for the  $j^{\text{th}}$  cluster of the  $i^{\text{th}}$  state,  $\boldsymbol{\gamma}_{1ij}$  is the cluster-level random-effect coefficients and is common to all  $m$ , and  $\boldsymbol{\gamma}_{2mijk}$  is the subject-level random-effect coefficients associated with the parameter  $\beta_m$  for the  $k^{\text{th}}$  subject within the  $j^{\text{th}}$  cluster. The random effects are assumed to follow a multivariate normal distribution with mean zero. Because the vector  $\mathbf{x}_{mijk}$  may include subject-level, cluster-level and state-level exposure variables, the fixed effects parameter vectors  $\boldsymbol{\beta}_1$  and  $\boldsymbol{\beta}_2$  represent the effects of different exposure variables on the annual changes in the pre- and post-periods. Thus, we may perform statistical tests to examine whether there are differences in trends between the pre- and post-periods overall and for each state, and whether the patterns of changes differ between the states.

Similarly for a count outcome  $Y_{ijkt}$  (e.g., number of clinical visits), we define the expected value  $\mu_{ijkt} = E(Y_{ijkt})$  and apply a Poisson regression model based on the natural log link function. The log expected number of clinical visits,  $\log(\mu_{ijkt})$ , can be modeled with the aforementioned segmented mixed-effects model. The use of an offset term in the models yields the estimates of the rate of clinical visits rather than the mean number of visits. The fixed-effect parameters,  $\beta_1$  and  $\beta_2$ , represent the effects of exposure variables on the annual changes in log of incidence rates for the pre- and post-periods, respectively. For a continuous outcome  $Y_{ijkt}$ , we will model the mean,  $\mu_{ijkt} = E(Y_{ijkt})$ , with the mixed-effects model and the parameters  $\beta_1$  and  $\beta_2$  indicate the effects of exposure variables on the annual changes in the outcomes for the pre- and post-periods, respectively. All final statistical models will be assessed with respect to the goodness-of-fit and the appropriateness of model assumptions. Statistical software SAS 9.4 and R environment will be used to implement the proposed analyses.

Furthermore, we will use the similar models as described above to evaluate post-policy impact of obesity screening and counseling (number of visits) on the outcomes such as weight loss, diabetes incidence, and diabetes outcomes (including hemoglobin A1c, controlled blood pressure, use of a statin medication). The outcome data collected after the universal coverage change (i.e.,  $t = 0, 1, \dots, 6$ ) will be used to estimate the trend of change. The number of screening and counseling will be used as a predictor in the mixed effects models. The effects of patient and practice characteristics will also be examined in the models. Statistical software SAS 9.4 and R environment will be used to implement the proposed analyses.

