## 1.0 Objectives

The overarching goal of this proposal is to understand the comparative effectiveness of obesity counseling as covered by Centers for Medicare and Medicaid Services (CMS) in improving weight loss for adults either with or at high risk of type 2 diabetes. CMS and most insurers now include obesity screening and counseling benefits, with no cost sharing to patients. Since overweight patients are at highest risk for diabetes, improved weight management services could prevent diabetes and its negative health outcomes. Beneficiaries with obesity are eligible for up to 20 face-to-face visits for weight counseling in the primary care setting. We propose comparing weight and diabetes outcomes in three states using electronic health record (HER) and claims data before and after this policy was implemented. The PaTH network brings together six academic health systems – the University of Pittsburgh/University of Pittsburgh Medical Center, Penn State College of Medicine/Hershey Medical Center, Temple University School of Medicine/Temple Health, and the Johns Hopkins University/Johns Hopkins Health System/Johns Hopkins Health Care, Geisinger Health Systems, and The University of Utah – to function as an integrated research network and learning health system, providing an infrastructure for observational studies, such as the one proposed here, that require populations beyond a single health system to answer important patient-centered health services questions ([www.pathnetwork.org](http://www.pathnetwork.org)). Using the PaTH Clinical Data Research Network (CDRN) infrastructure, we propose the following specific aims:

**Aim 1: Evaluate the impact of universal preventive service coverage for obesity screening and counseling on weight loss, diabetes incidence, and diabetes outcomes, in patients with diabetes or at high risk for diabetes (defined by body mass index (BMI)  $\geq 25$ ).** We will determine how the annual probability of receiving obesity and/or nutritional counseling (as defined by Current Procedural Terminology (CPT) code) changed pre- and post-policy across all insurers in a cohort of patients with diabetes and at high risk for diabetes. We hypothesize that individual patients are more likely to receive counseling following coverage implementation. Further, we hypothesize that patients who receive a greater number of face-to-face visits will have greater weight loss compared to those who receive fewer visits.

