## 2.0 Background

### 2.1 Scientific Background and Gaps

Overweight and obesity are America's number one health concern. The prevalence of obesity in the US is greater than 36%, which is far above the Healthy People 2020 objective of less than 30.5%. Perhaps most concerning is the rate that obesity has increased, having doubled since 1970. As the second most preventable cause of death, obesity is a risk factor for diabetes, cardiovascular disease, stroke, and cancer, all major causes of death in the US. Addressing obesity through lifestyle interventions decreases the risk of developing type 2 diabetes, a disease which affects over 29 million people (9.3% of the US population). Diabetes is associated with serious complications, including cardiovascular disease, blindness, renal failure and lower extremity amputation. Although complications are preventable with proper medical and lifestyle management, including weight loss, nearly half of patients with diabetes do not have adequate glycemic control.

Primary care clinics may be an ideal setting for weight control interventions. Greater than 80% of Americans see a PCP regularly and access to primary care is expected to increase with health care reform. Further, as PCPs identify and treat the multitude of conditions affected by being overweight, including diabetes, they are ideally positioned to best engage their patients in weight management. The Centers for Medicare and Medicaid Services (CMS) implemented a healthcare procedure coding system code for intensive behavioral therapy (IBT) for obesity within primary care settings in 2012 to facilitate payment for addressing obesity, which was followed by universal coverage by insurers for IBT for adults of all ages in 2013. However, the impact of this coverage on patient-centered outcomes is largely unknown.

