***Diabetes Cohort Definition.*** During year 1 of the proposed project, the investigative team, in collaboration with the PaTH Network, will identify a valid cohort of patients with type 2 diabetes. The cohort of patients under study will be defined as all patients age 18 and older with an indication of type 2 diabetes during the proposed study time frame. Patients will be classified as having diabetes using a clinically validated algorithm: type 2 diabetes mellitus on the problem list, diabetes-specific medications, hemoglobin A1c (HbA1c) results > 7.0%, or one inpatient diagnosis code or two outpatient diagnosis codes for type 2 diabetes (ICD-9 codes 250.xx). The diabetes cohort will be further limited to patients who will likely be captured in the PaTH EHR records or claims data so that outcome assessments can occur. Thus, we will further limit the diabetes cohort to patients who have either: (1) had at least 2 outpatient primary care visits in one of the PaTH health systems in the past 3 years (since January 1, 2012), or (2) for whom claims data are available. The cohort will be dynamic, with new patients added into the cohort after 2015 as they meet the diabetes cohort definition prospectively. The observational period for the outcome variables will be for the 10-year period from 2009-2019, thus including 3 years of data prior to the first policy change (CMS instituting coverage for intensive behavioral therapy for obesity) and 3 years after the last policy change (Pennsylvania Medicaid expansion) under study.

Following the definition of the diabetes cohort and key diabetes outcomes and covariates as described above, an initial extraction of variables will be conducted in Year 2 of the proposed project for years 2009-2015. This early data extraction from the PaTH Network will allow for cohort validation and data cleaning and editing, as well as required programming and determination of the analysis models. We will utilize this initial data extraction in Years 2 and 3 to analyze the impact of early health policy changes, as well as to prepare a manuscript of both the protocol and early findings of policy impact. The final data extraction will occur during the final quarter of Year 4 of the proposed project, allowing for completion of a ten-year time period (2019).

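### The IBT-coverage effect is read from a slope change at one knot, with no concurrent comparison and other policies in the same window; the written time axis also does not fit the coverage dates

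*Combined protocol and SAP*

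**What the plan says.** Section 8.0 fits a segmented mixed model to yearly individual outcomes, with one slope before and one after the policy change, joined at t = 0. It states that "the change in the trend/slope post-policy implementation may reveal the actual impact of the new policy controlling for baseline level and trend" and adds: "Such modeling strategies share the same spirit of interrupted time series analysis". The time index runs from -5 to 5, and the section notes that "An individual subject may not be in the system for all 11 timepoints of measurement".

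The policy dates are spread over several sections:
- Section 2.1, on the first step by CMS, names a new billing item: "intensive behavioral therapy (IBT) for obesity within primary care settings in 2012 to facilitate payment for addressing obesity".
- Section 2.1, on the other payers, dates their step one year later: "which was followed by universal coverage by insurers for IBT for adults of all ages in 2013".
- Section 8.0: "We set year 2014 as time origin for Utah when considering the policy impact of the ACA".
- Section 7.2: the observation period is 2009-2019 and includes "3 years after the last policy change (Pennsylvania Medicaid expansion) under study".

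On who may use the benefit, Section 1.0 says: "Beneficiaries with obesity are eligible for up to 20 face-to-face visits for weight counseling in the primary care setting". The at-risk cohort in Sections 3.1 and 7.2 starts at BMI 25.

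The plan also has contrasts within the data. Section 8.0 allows tests of trend changes overall, by state and between states. Section 2.2 values Utah as a state without Medicaid expansion. The subgroup analyses split patients by insurance history, and a secondary propensity-score analysis is planned. For the post-policy counseling analysis, Section 8.0 uses t = 0 to 6.

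**The concern.** Aim 1 asks what coverage of obesity counseling did. A slope change at one date answers that only if nothing else altered the trend around the same time, or if a group not exposed to the coverage shows what would have happened without it. The plan's own dates rule out the first condition, and no such group is named.

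At stake is attribution. If insurance expansion changed visit rates, weight recording or diabetes control, part of that change would appear as an effect of counseling coverage. This is bias, so more than two million patients do not reduce it; they make a misattributed slope look precise.

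The second problem is the origin. The model as indexed does not place its knot at either coverage date, so even without competing policies the IBT slope change would be misestimated.

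**Working it through.** **1. Inputs.** Window 2009-2019, 11 annual points (Sections 7.2 and 8.0). IBT coverage 2012 and 2013 (Section 2.1). ACA origin 2014 (Section 8.0). The year of Pennsylvania expansion is not stated; three years of data after it, ending in 2019, gives 2019 - 3 = 2016. Because this is inferred, I use 2014, 2015 and 2016 for the competing policy.

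**2. Which origin the written index fits.** Subtracting the origin from 2009 and 2019:
- origin 2012: t = -3 to 7
- origin 2013: t = -4 to 6
- origin 2014: t = -5 to 5

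So -5 to 5 fits only 2014, while the later 0 to 6 implies 2013. Section 8.0 does say that the years before and after may vary by policy, but it gives no origin for IBT coverage.

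**3. Competing slope change, no true IBT effect.** Let P_c = max(0, year - c), and let r(.) be the residual after regression on an intercept and linear year. With the knot at 2013 and a competing slope change of 1 unit per year from year c, the least-squares slope change is r(P_2013)·r(P_c) / r(P_2013)·r(P_2013). The denominator is 6.364.

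| Competing policy starts | Numerator | Credited to the 2013 knot |
|---|---|---|
| 2014 | 6.364 | 1.00 |
| 2015 | 5.455 | 0.86 |
| 2016 | 4.000 | 0.63 |

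**4. Competing level jump instead.** A jump of 1 unit from year c equals P_(c-1) - P_c, so the estimate is the difference of two successive shares (the share for c = 2013 is 1):
- 2014: 1.000 - 1.000 = 0.00
- 2015: 1.000 - 0.857 = 0.14
- 2016: 0.857 - 0.629 = 0.23

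These are units per year per unit jump.

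**5. Knot at 2014, true IBT slope change of 1.0, no competing policy.** The denominator is r(P_2014)·r(P_2014) = 7.045. If the change starts in 2013, the estimate is 6.364/7.045 = 0.90. If it starts in 2012, it is 4.818/7.045 = 0.68.

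**6. Is a second knot enough?** VIF = 1/(1 - R²), with R² the squared correlation of the two residualized terms:
- 2013 and 2014: R² = 0.903, VIF 10.3
- 2013 and 2015: R² = 0.735, VIF 3.8
- 2013 and 2016: R² = 0.549, VIF 2.2

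Without a comparison group, the 2013 and 2014 terms are close to collinear.

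**7. What a comparison group could do.** The site counts in the Section 7.2 table add up to its totals: 2,062,499 at risk, of whom 944,655 have BMI 25-29.9 (944,655/2,062,499 = 45.8%). The 30+ bands sum to 592,741 + 312,277 + 211,363 = 1,116,381. If the 25-29.9 band feels a share s of the competing policy, the bias in step 3 is multiplied by (1 - s):
- s = 1: 0
- s = 0.75: 0.25, 0.21, 0.16
- s = 0.5: 0.50, 0.43, 0.31

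**The case against.** A reader might infer three stronger things that the documents do not support.

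**That the plan has one undifferentiated series and declares the slope change to be the effect.** It says only that the slope change may reveal the impact. It also has between-state tests, a non-expansion state, subgroups by insurance history and a propensity analysis. Patients insured throughout are a fair partial answer to insurance expansion, which Section 7.2 treats as a policy under study. What remains is narrower. Coverage is described as universal, so a contrast with Utah speaks to Medicaid expansion and differences the IBT effect out. Patients never insured are not used as a comparator, and they differ on the very factor that expansion changes. Propensity scores balance patient characteristics, not calendar time.

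**That BMI 25-29.9 is a ready-made ineligible control.** The plan gives no BMI cut-off for the benefit and nowhere calls that band ineligible. Aim 1 also counts nutritional counseling, which is not restricted to obesity. The at-risk cohort uses the most recent weight, so a patient who lost weight after counseling could move into the band. Table 1 defines weight loss between IBT visits, which leaves it undefined for patients without such visits. These points stand, and they are why the contrast belongs in a supporting role.

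**That the whole estimate would be misattributed.** The 1.00 holds for a slope-type change in 2014. A level jump in that year gives 0.00. No size for any competing effect is given, so the actual bias is unknown.

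**Conclusion.** The concern holds in a limited form. As written, the slope change cannot separate IBT coverage from other policies in 2009-2019, and the planned state, insurance and propensity analyses do not close that gap. The possible misattribution runs from none (a level jump in 2014) to all of a competing slope change (one starting in 2014), with 0.63 for a slope change starting in 2016. Separately, a 2014 knot would recover only 0.68 to 0.90 of a true IBT slope change.

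These figures assume a linear scale, noise-free annual means, all 11 years present and a single competing policy. They illustrate the mechanism and do not estimate the bias in this study. The 2016 date is inferred. The two time indices in Section 8.0 need to be reconciled whatever is decided about a comparison group.

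**What to change.** 1. **Knots and origins.** For the IBT-coverage estimate, set the knot by payer (Medicare 2012, other insurers 2013) and make the two time indices in Section 8.0 agree. Add separate terms for the ACA and for Medicaid expansion, dated by state. Note that the 2013 and 2014 terms are nearly collinear without a comparison group (VIF about 10).

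2. **Supporting controlled analysis in the at-risk cohort.** Pre-specify a BMI-group (30+ against 25-29.9, classified on pre-policy BMI) by segment interaction. Use yearly outcomes defined for both groups, such as receipt of counseling, yearly weight and diabetes incidence, and include a check of pre-policy trends.

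3. **Reporting.** Describe the uncontrolled slope change as an association with the period unless the controlled analysis agrees.

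**Cost.** For the at-risk cohort, this needs SAP wording, model terms and a pre-policy BMI classification. The diabetes cohort would need BMI added, since the bands are tabulated only for the at-risk cohort.

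**Downsides to state in the SAP.**
- Lower eligibility of the 25-29.9 band is an inference from Section 1.0.
- Spill-over of counseling into that band would shrink the contrast.
- Regression to the mean can mimic a slope change, so an early pre-policy BMI is preferable.
- Only 3 to 4 pre-policy points are available to check trends.
- The cohort is dynamic, so patients without a pre-policy BMI drop out of this analysis.

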*Statistical Power.* Given the very large sample sizes that are anticipated for the research studies (more than 320,000 patients with diabetes and 2,000,000 patients at-risk for diabetes), there is tremendous statistical power to detect very small effect sizes for individual-level exposure variables. Therefore, the clinical investigators on this project will need to

examine each statistically significant result and determine whether it is clinically significant. Furthermore, such large sample sizes ensure the robust estimation results from the proposed multi-level statistical modeling which involves large number of regression coefficient and covariance parameters. The major benefit of the large sample size for each research study is that it provides sufficient statistical power for investigating effects of interest within subgroups that might be constructed according to age, race-ethnicity, cohort decompositions, etc.

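### The segmented policy model has no calendar-year or cluster-by-year error term, so the standard error of the pre/post slope change shrinks with patient numbers although the contrast rests on 11 shared years

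*Combined protocol and SAP*

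**What the plan says.** Section 8.0 (Statistical Plan) fits multi-level mixed models to yearly patient records and likens this to interrupted time series analysis. It contrasts the classical single long series with its own data: "we have a large number of short series from each individual subject, namely, longitudinal data". The policy effect is the slope contrast: "the change in the trend/slope post-policy implementation may reveal the actual impact of the new policy controlling for baseline level and trend". Formal testing is foreseen: "we may perform statistical tests to examine whether there are differences in trends between the pre- and post-periods overall and for each state".

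The model runs over t = -5 to 5, and "An individual subject may not be in the system for all 11 timepoints of measurement". Section 7.2 sets the calendar window: "The observational period for the outcome variables will be for the 10-year period from 2009-2019". Counting both end years gives 11 calendar years, which matches t.

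Four levels are named: yearly measurement, subject, cluster and state. The equation has two kinds of random term. One is a cluster effect (gamma_1ij), stated to be shared by all three coefficients m = 0, 1, 2. The other is a set of subject effects (gamma_2mijk), one per coefficient. "The random effects are assumed to follow a multivariate normal distribution with mean zero". State has no random term, and no random term carries the index t.

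The Statistical Power paragraph says that, with more than 320,000 patients with diabetes and 2,000,000 at risk, "there is tremendous statistical power to detect very small effect sizes for individual-level exposure variables". It gives no alpha, effect size or degrees of freedom.

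**The concern.** The policy is an exposure of calendar time. Section 2.1 dates the counseling benefit to 2012 for CMS and 2013 for all insurers, so it is not staggered by state. Everyone crosses the knot together, and the slope change is learned from how 11 yearly levels lie around two joined lines.

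A departure from those lines that patients share in a given year does not average out as patients are added. The plan itself points to possible sources. Medicaid expansion falls inside the window. New patients enter the cohort after 2015. Uncontrolled diabetes counts a missing A1c as a failure (Table 1), so a year's change in testing practice would move it. The specified model has nowhere to put such a departure except patient-level noise, which it divides by a very large N.

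At stake is error control for the pre/post policy tests, including the Aim 1 question of whether counseling receipt rose after coverage.

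**Working it through.** **Inputs from the documents.** Time points t = -5 to 5 (section 8.0). Diabetes cohort count from the section 7.2 table: 25,219 + 150,589 + 60,324 + 40,536 + 51,787 = 328,455, which reproduces the stated total. There is no power figure to reproduce.

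**Assumptions not in the documents.** Two-sided alpha 0.05; probability of control p = 0.7; all patients seen in all 11 years; no between-subject spread in slope change; year-shock SD s = 0.01, 0.02 or 0.05 logits. At p = 0.7, multiplying by p(1 - p) = 0.21 turns these into about 0.2, 0.4 and 1 percentage point.

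**Step 1: the cluster term drops out.** Put a common cluster contribution g into all three coefficients.
- Pre-period: g + (t + 5)g = (t + 6)g.
- Post-period: g + 5g + tg = (t + 6)g.

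This is one straight line with no kink at t = 0, so it adds nothing to the variance of beta_2 - beta_1. Only subject-level terms remain, and they average out as 1/N.

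**Step 2: standard error under the planned model.** With regressors 1, t and max(t, 0), the slope-change element of (X'X)^-1 is c = 0.1419.
- Yearly variance: v = 1/[N p(1 - p)] = 1/(328,455 × 0.21), so sqrt(v) = 0.0038.
- SE = sqrt(c v) = 0.377 × 0.0038 = 0.0014 logits per year.

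For the same 11 years, the SE is 0.0260 at N = 1,000, 0.0082 at 10,000, 0.0037 at 50,000 and 0.0006 at 2,062,499. Allowing a subject slope-change SD of 0.3 raises the value at 328,455 only to 0.0015.

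**Step 3: add a shared year shock.** If K equal-sized groups have independent shocks (K = 1 means one shock common to all), the true variance is c(v + s²/K). The term c s²/K does not depend on N. The true SE exceeds the planned SE by the ratio R = sqrt[1 + s²/(K v)], and the false-positive rate is 2[1 - Phi(1.96/R)].

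For K = 1 and N = 328,455, R = 2.8, 5.3 and 13.

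| Patients per year | Shock structure | s = 0.01 | s = 0.02 | s = 0.05 |
|---|---|---|---|---|
| 328,455 | common to all sites | 49% | 71% | 88% |
| 328,455 | independent, six equal systems | 18% | 41% | 72% |
| 50,000 | common to all sites | 17% | 39% | 71% |
| 50,000 | independent, six equal systems | 7% | 13% | 40% |
| any | no shock (s = 0) | 5% | 5% | 5% |

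A common shock SD of about 0.0025 logits (0.05 percentage points) already doubles the error rate to 10% at 328,455.

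**Step 4: position of the knot.** Moving the origin to 2013 (t = -4 to 6) or 2012 (t = -3 to 7) raises c to 0.157 or 0.218. Because c cancels from R, the rates above do not change, but the SE itself is larger.

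**Step 5: do the remedies work?** Simulation with no policy effect, six equal systems, N = 328,455, p = 0.7 and a common shock:
- Ordinary segmented regression on the 6 × 11 = 66 system-by-year cells, with system intercepts, rejected about 33%, 43% and 47% for the three shock sizes. The common shock repeats in every system, so the cells are not independent.
- Segmented regression on one pooled yearly series, with 11 - 3 = 8 df, rejected about 5% throughout.

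**The case against.** **The size is unknown.** The documents give no year-to-year variation, and with none the planned test is valid. A reader might infer that policy intervals are certainly far too narrow, or that nearly every outcome will show a false effect. The documents do not support that. What they do show is that the model has no way to detect or absorb shared variation if it exists.

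**The common-shock, full-N row is the unfavourable end.** Table 3 lists different EHR platforms, so some shocks would be local, and clinics may serve as clusters. The 328,455 is a count by diagnosis code before the visit-or-claims restriction, in a dynamic cohort. These points stand, and the lower rows of the table reflect them. Many clinics with independent shocks would reduce the inflation further. State-specific origins, such as 2014 for Utah, give some staggering for the ACA analysis, but not for the counseling benefit.

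**The plan has safeguards.** It mentions serial correlation as something mixed models can handle, promises checks of fit and assumptions, plots yearly means, and asks investigators to judge clinical significance. These make an unnoticed error less likely. However, no shared-year structure, check or remedy is named, and a judgement of clinical relevance does not widen an interval.

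**The wording could be over-read.** The sentence about many short series contrasts data structures; it does not claim that they beat a single series. The power sentence is limited to individual-level exposures and is not wrong in itself. The later sentence on power within subgroups is broader and could be taken to cover the policy contrast.

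**Not all of Aim 1 is affected.** Its second hypothesis, more visits and more weight loss, compares patients, as does the section 8.0 analysis by number of visits. A reader might extend the point to these, but their contrasts do not rest on the pre/post slope change.

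**Conclusion.** The point holds for the pre/post policy tests. As specified, the slope-change standard error falls as 1/sqrt(N) with the number of years fixed at 11, and nothing else in the plan corrects this.

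The missing term can be read directly from the equations. The size of the consequence rests on assumed shock sizes, 70% controlled and a balanced cohort. On those assumptions, the false-positive rate at nominal 5% runs from 7% (50,000 patients, small independent shocks) to 88% (328,455 patients, larger common shocks). It is 5% if no shared variation exists. The calculation uses controlled diabetes, the plan's own example outcome; rates for counseling receipt would depend on that outcome's base rate and year-to-year variation.

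**What to change.** For the policy slope-change test, add to the section 8.0 model a calendar-year random effect and a health-system-by-year (or clinic-by-year) random effect, with small-sample degrees of freedom based on the number of years. State alpha and the degrees of freedom.

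Two alternatives are acceptable:
- Run the segmented regression on one pooled, case-mix-adjusted yearly series, with 8 df.
- Run it on system-by-year values, but only if the second stage keeps a common-year random component. Ordinary regression on those cells is not enough, as step 5 shows.

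In the Statistical Power paragraph, add that the large N gives power for individual-level exposures and not for the policy slope change, including within subgroups.

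The cost is SAP wording and extra random terms or a second-stage regression; no new data are needed. The downside is wider, less favourable confidence intervals for the policy effect.
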